 - Higher levels of reassurance of the benign nature of MSKP.
 - More adaptive MSKP coping and psychological flexibility.
 - Higher self-reported levels of physical activity.
 - More positive global ratings of change.
 - Lower number of healthcare visits, referrals for diagnostic imaging and to specialist/tertiary care for MSKP, lower analgesic medication use, fewer sick leave days and lower direct costs.
 - More positive and concordant patient and physiotherapist evaluations of MSKP-related shared understanding, communication, participation, involvement and emotional support at the initial physiotherapy consultation.
2. Improvements in MSKP illness perceptions and higher levels of reassurance of the benign nature of MSKP mediate improved pain intensity and pain self-efficacy as a result of exposure to the PainSMART-strategy compared to usual physiotherapy management alone.

Null hypothesis (H0): no statistically significant or clinically relevant differences between the intervention group (PainSMART-strategy as an adjunct to usual physiotherapy management) and the control group (usual physiotherapy management alone).

Exploratory research questions:

1. What baseline factors are predictive of improved patient outcomes after exposure to the PainSMART-strategy?
2. What baseline factors are predictive of the persistence of MSKP?
3. What type of psychological factors and strategies are associated with patient outcomes after exposure to the PainSMART-strategy?

4. Is pain self-efficacy a potential mediator of the PainSMART-strategy's effect on health outcomes?
5. What are patients and physiotherapists experiences of the PainSMART-strategy?

Primary research question for the qualitative phase of the research program:

- Does exposure to the PainSMART-strategy influence communication around pain at the initial physiotherapy consultation?

Dimensions to explore via the qualitative phase of the research program:

- Describe how physiotherapist and patient participants incorporate the PainSMART-strategy into the initial physiotherapy consultation.
- Explore potential explanations for the quantitative results of the randomized controlled trial (RCT).
- Describe the participating patients' understanding of MSKP and explore how this may relate to the PainSMART-strategy's theoretical underpinnings.
- Explore if patients' understanding of MSKP diverge from the understanding of the physiotherapist during the initial consultation.

Methods

Trial design

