All patients randomised to the intervention group (PainSMART) will receive the PainSMART-strategy as an adjunct to usual physiotherapy management. The physiotherapists who discuss the film at the initial physiotherapy consultation are all registered physiotherapists employed at one of the five participating physiotherapy departments ($n =$ approx. 130). All participating physiotherapists will have seen the film and received written and verbal information about the study, and their role in the study, prior to the start of patient recruitment. No incentives are provided to the physiotherapists to take part in the study.

Table 2: Content in the film addressing the illness perception dimensions in the Common-sense model of self-regulation (CSM) (Leventhal et al., 2016).

CSM dimension	Key messages presented within the film
Identity	
 Pain doesn't necessarily mean damage and pain is a protective system that is necessary and often helpful.
Timeline	
 Pain can improve and change over time, irrespective of how long you have had your pain. Many pain problems resolve by themselves, but it can take time.
Consequences	
 Pain does not need to stop you from working, exercising or taking part in valued activities. But it can signal that you need to make some adjustments in your life.
Causes	
 Pain is very rarely caused by serious pathology. Pain is not always caused by injury. Pain can also be caused by physical overload, inactivity, imbalance in life or a combination of these factors.
Control	
 You can influence your pain through your thoughts and actions but support is available from healthcare professionals. You can act to improve your pain by staying active, adjusting sleep and diet if necessary.
Emotional representations	
 Your thoughts and feelings towards your pain and your mental health influence your pain experience.

Where and how

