The intervention group will be exposed to the film on two occasions. Access to the film is imbedded within the intervention group's online questionnaires and the film is first made available immediately following completion of baseline background and PROM data collection. Further exposure occurs at the data collection time point prior to the initial physiotherapy consultation. The time from baseline to the initial physiotherapy consultation will vary for each participating patient depending on clinical prioritisation and the accessibility of initial consultations at the participating physiotherapy departments. The film is hosted on RÖ's Quick channel, viewable on any electronic device and is exclusively available to the intervention group via the questionnaires. In order to reduce the risk of contamination bias the film is not shareable or available via online searching.

All participating physiotherapists will provide initial consultations to patients in both the intervention and control groups. For the intervention group the initial physiotherapy consultations will take place as usual with the addition of the discussion around the film and questionnaires. Any tailoring of the physiotherapists' responses to the patients' answers will occur according to the preferences and skills of each individual physiotherapist. The physiotherapists will not have access to the results of the questionnaires completed by the patients prior to the initial consultation.

Why

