on generalisability (Mercieca-Bebber et al., 2018). All outcome data will be compared based on the ITT principle. This means that all patients that have been randomised remain in the analysis based on their group allocation. In the event of substantial missing data, evaluation of the mechanisms for missing data will be used (Enders, 2011). Missing data will otherwise be handled under the missing at random assumption (Enders, 2011). Multiple Imputation or Maximum Likelihood estimation will be used assuming that missing data is conditional on variables included in the model. Imputation method considering missing at random or not missing at random will be used in the ITT analysis. Patients who cancel their initial physiotherapy consultation will be excluded from the PREM analysis but will remain in the study for PROM and healthcare register data analyses.

Study monitoring and harms

There will be no data monitoring committee since the study is independent from the sponsor and the intervention is implemented as an adjunct to usual physiotherapy management with low risk for unexpected adverse events. The PROMs included in the study are sensitive to worsening in the patients' condition. An internal pilot interim analysis was planned and conducted (February 29th, 2024) after approximately 50% of the initially planned sample (n = 229) had consented to the study and reported outcomes at time point two (72-24 hours prior to the initial physiotherapy consultation) and three (24 hours post the initial physiotherapy consultation). This interim analysis enabled evaluation of the viability of the a-priori sample size calculation and the recruitment frequency. The analysis utilised linear mixed models to investigate between group differences (effect size) for change from baseline to time points two and three for outcome. The significance level for the interim analysis was p=0.05. After interim sample size calculation, the sample size was adjusted slightly to take loss to follow-up into account. The sample size calculation is described under the protocol heading sample size. The trial would have been stopped if the internal pilot interim analysis could not be performed due to not attaining 50% of the sample size at Time point two and three within six months. No further interim analyses are planned.

Ancillary and post-trial care

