- More positive and concordant patient and physiotherapist evaluations of MSKP-related shared understanding, communication, participation, involvement and emotional support at the initial physiotherapy consultation.

2. Improvements in MSKP illness perceptions and higher levels of reassurance of the benign nature of MSKP mediate improved pain intensity and pain self-efficacy as a result of exposure to the PainSMART-strategy compared to usual physiotherapy management alone.

The null hypothesis (H0) is that there is no clinically or statistically significant differences between the intervention (film) group and the control group (usual physiotherapy management).

Secondary exploratory research questions

1. What baseline factors are predictive of improved patient outcomes after exposure to the PainSMART-strategy?
2. What baseline factors are predictive of the persistence of MSKP?
3. What type of psychological factors and strategies are associated with patient outcomes after exposure to the PainSMART-strategy?
4. Is pain self-efficacy a potential mediator of the PainSMART-strategy's effect on health outcomes?
5. What are patients and physiotherapists experiences of the PainSMART-strategy?

Study Methods

Trial design

This is a two-armed, parallel group, randomised controlled trial in which the intervention group (PainSMART-strategy + usual physiotherapy management) will be compared to a control group (usual physiotherapy management). Treatment allocation is a 1:1 ratio. The control group and statistician will be blinded. One independent statistician will be blinded for the primary analyses. Another independent statistician will be responsible for database development and linkage of patient and physiotherapist data. The PainSMART-strategy is described in full in the trial protocol.

Randomisation

A computerised randomisation sequence for 800 patients into group A (Intervention group) or B (Control group) has been generated by a blinded statistician using SPSS prior to the start of patient recruitment. Participating patients will be allocated to intervention or control group based on the order of their inception to the study. The randomisation is described in full in the trial protocol.

Framework

The trial's hypotheses apply a superiority testing framework where the PainSMART-strategy is hypothesized to be superior in outcome compared to control.

Determination of Sample size

The sample size calculation is described in full in the trial protocol.

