Patients receive seven questions and physiotherapists 3 questions regarding their experience of the initial physiotherapy consultation. Between group mean difference for responses to these questions will be analysed using independent sample t-tests. These analyses will be presented as mean and SD for each group and the between group difference in mean and CI. Three of the patient questions will be analysed for concordance with the matched physiotherapists' questions. Concordance within the intervention group and control group will primarily be analyzed by calculating intraclass correlation coefficient (ICC) with 95% confidence interval on each question as well as all three questions combined. Two-way random effects model will be used for ICC, assuming raters to be randomly selected. The ratings are single measures analyzed for consistency, to measure systematic differences between ratings. Patients and physiotherapists are treated as two independent raters, rating each of the three questions.

Sensitivity analyses

The following are all re-analyses of the primary and secondary outcomes under different conditions:

- Per-protocol analysis
- Complier average causal effect (CACE) analysis
- Responder analysis
- Complete case analysis (in case of >5% missing data)

Per-protocol analysis

Per-protocol analyses for the primary and secondary outcomes will be conducted to assess robustness of the ITT analyses and to further inform decisions regarding superiority. The sample of the patients for the per-protocol analyses will be as follows:

- Intervention group: patients receiving the PainSMART-strategy with no or minor deviation from protocol.
- Control group: patients receiving intervention with no or minor deviation from protocol.

Data on the physiotherapists' self-reported adherence to the protocol will be cross-referenced with the intervention respective control group patient consultations that each physiotherapist has conducted. This, in combination with the intervention group patients' self-reported exposure to the film, will provide data on deviation from protocol.

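### The consultation-experience (PREM) comparison is an unadjusted t-test among patients who attended and responded; attendance is settled after the film, so the difference is not fully protected by randomisation

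*Protocol*

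**What the plan says.** **Status.** The SAP lists this under the hypotheses for confirmatory research questions: "More positive and concordant patient and physiotherapist evaluations of MSKP-related shared understanding, communication, participation, involvement and emotional support at the initial physiotherapy consultation". The protocol's Hypotheses section does the same.

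**Who is analysed.** Protocol, Missing data: "Patients who cancel their initial physiotherapy consultation will be excluded from the PREM analysis but will remain in the study", the latter for PROM and register outcomes. The SAP defines an intention-to-treat and a per-protocol population, but no attender population for the PREMs.

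**How.** SAP, Patient and physiotherapist experience outcome analyses: "Between group mean difference for responses to these questions will be analysed using independent sample t-tests". That section names no covariates, although the SAP considers covariate adjustment for the continuous PROM outcomes and most register outcomes. Concordance between patient and physiotherapist is analysed by intraclass correlation within each arm.

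**Order of events.** Protocol, Where and how: "the film is first made available immediately following completion of baseline background and PROM data collection". It is offered again at the time point 24 to 72 hours before the consultation.

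**What is already planned.** The SAP's flow diagram counts cancelled consultations and PREM numbers analysed in each arm. Its Missing data section compares baseline characteristics and PROM scores of patients with and without missing data.

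**The concern.** A patient enters the PREM comparison only if the consultation took place and the rating was returned. Both conditions are settled after randomisation and after first access to the film, so allocation could influence them.

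The documents give reasons for an influence in each direction:

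- **Towards cancelling.** Table 2 of the protocol includes the message "Many pain problems resolve by themselves, but it can take time", alongside reassurance about serious causes and advice on self-management.
- **Towards attending.** The film's third section prepares patients for the consultation. Table 2 also says that professional support is available. Only intervention patients are told that they will discuss the film with the physiotherapist.

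If the arms lose different kinds of patient, part of a PREM difference may reflect who was rated and not what happened in the consultation. It would still be reported under a confirmatory hypothesis.

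**Working it through.** The plan states no figure for cancellation or for the PREM difference, so there is nothing to reproduce. The steps below size the possible effect. Attendance rates, rating SD and selection strength are assumptions; arm size and response come from the Protocol, Sample size.

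**1. Precision.** 450 patients at baseline, 1:1, gives 225 per arm. The response reported there for time point 3 is about 90%, and 225 × 0.90 ≈ 200. The standard error of the difference is √(2/200) = 0.10 SD. If 5% and 10% also cancel, the numbers are 225 × 0.95 × 0.9 = 192 and 225 × 0.90 × 0.9 = 182, and the standard error is √(1/192 + 1/182) = 0.103 SD.

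**2. Worst case (trimming bound).** Assume normal ratings and that the film moves attendance in one direction only. The trimmed fraction is p = 1 − (lower attendance / higher attendance), and the largest shift is φ(z_p)/(1 − p).

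| Assumed attendance | p | Largest shift | In points if the SD is 2 |
|---|---|---|---|
| 90% v 87% | 3.3% | 0.077 SD | 0.15 |
| 90% v 85% | 5.6% | 0.119 SD | 0.24 |
| 90% v 80% | 11.1% | 0.213 SD | 0.43 |

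Equal response among attenders leaves p unchanged: (0.85 × 0.9)/(0.90 × 0.9) = 0.85/0.90. Unequal response changes it, so the bounds must be built on who has an observed rating and not only on who attended.

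**3. Moderate selection.** Let the tendency to attend have correlation ρ with the rating. The bias is ρ_film × λ(cancellation in film arm) − ρ_control × λ(cancellation in control arm), with λ(c) = φ(z_c)/(1 − c). This gives λ(0.05) = 0.109 and λ(0.10) = 0.195. False-positive rates use the SAP's 5% level for one-sided tests, with the bias favouring the film.

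- Cancellation 5% control, 10% film; ρ = 0.3 in the film arm only: 0.3 × 0.195 = 0.058 SD, false positives about 14%. A simulation of 4,000 trials gave 0.057 SD and 13.8%.
- Same rates, ρ = 0.3 in both arms: 0.3 × (0.195 − 0.109) = 0.026 SD, about 8%.
- Cancellation 5% in both arms, ρ = 0.3 in the film arm only: 0.3 × 0.109 = 0.033 SD, about 9%.
- No relation to the rating, or equal rates with equal selection: no bias, 5%.

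**4. Can an attendance test settle it?** For 90% v 85% with 225 per arm, the standard error is √[(0.90 × 0.10 + 0.85 × 0.15)/225] = 0.031. Then 0.05/0.031 = 1.61, and two-sided 5% power is Φ(1.61 − 1.96) ≈ 36%. A non-significant attendance difference is weak evidence of no selection. The third scenario in step 3 shows that even equal rates can hide different kinds of canceller.

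**5. Do the planned sensitivity analyses cover it?**

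- Per-protocol treats a cancelled consultation as a minor deviation and keeps the patient, who still has no consultation to rate.
- The CACE model uses the baseline score of the outcome, which a consultation rating lacks.
- The responder analysis needs change from baseline, which is likewise absent.
- Complete-case analysis keeps the same selected patients.

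**The case against.** The case for leaving the plan alone is substantial, and much of it stands.

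- **Exclusion is unavoidable.** A patient without a consultation has nothing to rate. A reader might see a contradiction with the protocol's statement that all randomised patients stay in the analysis. The same Missing data section names PREMs as the exception and keeps cancellers for the other outcomes, so it is a disclosed exception.
- **An effect on attendance is possible, not shown.** A reader might infer that the film makes patients cancel, and that the PREM difference is therefore biased. The documents give no attendance by arm, and they contain messages favouring attendance as well as messages against it. Nor is the control arm free of this filter, since the SAP's flow diagram expects control cancellations too.
- **The healthcare-visit hypothesis is weak support.** The hypothesis "Lower number of healthcare visits, referrals for diagnostic imaging and to specialist/tertiary care for MSKP" might be read as predicting fewer initial consultations. The self-reported visit count leaves out the study physiotherapist, so only the register count could include that visit.
- **Some reporting is planned.** Cancellations by arm and the missing-data comparisons will help a reader judge. They are descriptive, and neither is tied to how the PREM result is interpreted.
- **The bounds are extreme.** They put every additional canceller in one tail and assume normality for bounded 0 to 10 items. In the 5% v 10% scenario, moderate selection gives 0.026 to 0.058 SD, about a quarter to a half of the 0.113 SD bound for those rates.

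What remains is that a confirmatory comparison rests on a group formed after exposure, by a test that uses no baseline information, with nothing to show how far selection could move the result.

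**Conclusion.** The point holds as a gap in the analysis, not as a demonstrated bias. The PREM difference is not fully protected by randomisation, because attendance and response follow film exposure and could depend on allocation in either direction.

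Under assumed attendance gaps of 3 to 10 points from 90%, normal ratings and one-direction selection, the worst case is about 0.08 to 0.21 SD. The standard error is about 0.10 SD, so a 5-point gap could at worst shift the result by roughly one standard error. Under moderate selection the shift is smaller, and it is zero if attendance is unrelated to ratings. The true size and sign cannot be obtained from the documents.

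The concordance analysis is not a t-test but uses the same selected pairs. PREMs are secondary outcomes, and the primary outcomes keep patients who cancel. This is a worthwhile, inexpensive improvement and does not threaten the trial's main result.

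**What to change.** Amend the SAP section on patient and physiotherapist experience outcomes before the PREM data are analysed:

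1. Replace the t-tests with regression on arm, adjusted for baseline factors already collected (for example pain, PSEQ-10, BIPQ, reassurance, pain duration and age). State that this reduces selection but cannot remove any that works through worry or pain remaining after the film.
2. Report attendance and PREM availability by arm, with the difference and its confidence interval, and the baseline characteristics by arm of patients with an observed PREM.
3. Add trimming bounds for each PREM difference as a sensitivity analysis, based on who has an observed rating (consultation attended and rating returned). State the assumption that the film moves availability in one direction only; messages pulling both ways make it open to question.
4. State that the PREM result applies to attenders and interpret it alongside the bounds. Do not add a rule that waives this when attendance does not differ significantly.

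The cost is SAP wording and a short supplementary analysis, with no new data. The downside is a possibly weaker PREM claim.
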